**Inclusion:**

- Veterans, aged 50 to 90, of any racial or ethnic group
- Diagnosis of amnestic MCI based on Logical Memory of the Wechsler Memory Scale-IV (WMS-IV) and Functional Activities Questionnaire (FAQ)
- Available informant
- Visual and auditory acuity to allow neuropsychological testing
- Willingness to participate in exercise training + cognitive training program for 8 months duration
- *Musculoskeletal illness or injury (i.e., osteoporosis, degenerative disc or joint disease, arthritis) that would make weight-bearing exercise difficult*
- Approval by Primary Care Provider to participate in water-based physical exercise

**Exclusion:**

**Psychiatric Exclusions**

- Current, uncontrolled severe psychiatric disorder, such as Bipolar I, Schizophrenia, or Major Depressive Disorder as determined by the Mini International Neuropsychiatric Interview (MINI)
- Diagnosis of dementia, Clinical Dementia Rating Scale (CDR) > 0.5; modified Hachinski score  $\geq 4$ ; or delirium. Those veterans with scores indicative of dementia (CDR > 0.5, modified Hachinski  $\geq 4$ ) will be referred to the Memory Disorders Clinic at VAPAHCS for a full diagnostic work-up.

**Medical Exclusions**

- History of neurological (e.g., multiple sclerosis, seizure disorder, stroke,) or system illness affecting CNS function (e.g., liver failure, kidney failure, congestive heart failure, systemic cancer)
- Acute illness or unstable chronic illness, e.g., history of severe liver disease (cirrhosis, esophageal varices, ascites, portal hypertension, hepatic encephalopathy)
- Current severe cardiac disease (e.g., uncontrolled atrial fibrillation, defined as mean 24 hour heart rate  $>85$  beats/min, or 24 hour maximal ventricular rate  $>150$  beats/min; uncontrolled ventricular arrhythmias, defined as recurrent ventricular tachycardia  $>3$  beats in succession, or 24 hour PVC count  $>20\%$ ; active pericarditis or myocarditis; Class III/IV heart failure and / or ejection fraction  $< 20\%$ ; thrombophlebitis; pulmonary disease with a drop in O2 Sat with exercise to 90% without oxygen; embolism within past 6 months)
- Inability to participate in an exercise stress test
- Morbid obesity (BMI  $> 39$ )
- Inability to read, verbalize understanding and voluntarily sign the Informed Consent

**Justification of Inclusion / Exclusion Criteria.** The purpose of the inclusion and exclusion criteria is to provide a well-defined sample of older veterans with amnestic MCI that are appropriate for participation in both an

exercise training and cognitive training trial. The criteria chosen were based upon those used in prior studies of cognitive training with older adults with MCI (Yesavage et al., 2008) and those recommended by the American College of Sports Medicine (2006). Prior studies have used these criteria to successfully recruit veterans for cognitive training interventions (Yesavage et al., 2008) and exercise training interventions (Myers et al., 2010). Determination of inclusion and exclusion criteria will be based on veterans' responses to semi-structured clinical interviews (MINI and CDR), specific neuropsychological measures (Logical Memory of WMS-IV; CDR), functional assessment (FAQ), assessment of risk for vascular dementia (modified Hachinski score), a physical examination by a clinician, and a cardiopulmonary exercise test.

Recruitment Procedures. Participants will be recruited through clinician referral, media advertisement, and local veteran agencies. Other sources of recruitment include the ACRC and VAPAHCs outpatient clinics. Specifically, these outpatient clinics include but are not limited to those within the Sierra Pacific MIRECC (Geriatric Memory Clinic) and the VAPAHCs Psychology Service. Recruitment will be the responsibility of the PI and the exercise physiologists. [name] and staff will work closely with providers in these clinics and centers to identify potential participants as well as be available to speak with the veterans should they have questions about the study. Researchers in our center have a successful track record of recruiting subjects for cognitive training studies (Fairchild & Scogin, 2010; Yesavage et al., 2008) as well in exercise trials (Myers et al., 2010). We have strong ties with VA and community providers. These funds will be used to purchase "air time" on radio stations as well as print media to be used around the larger Bay Area community.

Study Procedures. Once recruited and successfully screened (i.e., Time 1 assessments), participants will meet with the study staff to develop an exercise prescription based upon the information obtained during the screening process. For the first two months of the exercise training, participants will attend thrice weekly exercise sessions at the VAPAHCs Aquatic Therapy Center. These training sessions will feature a combination of land-based stretching and water-based exercises to achieve the targeted cardiovascular training zone. *All pool-based exercise sessions will include five-minute warm-up and cool-down sessions prior to and following a combination of land-based stretching and water-based exercises to achieve the targeted cardiovascular training zone. These aquatic exercises will incorporate resistance training, functional exercise movements, and aquatic plyometric activities. Participants will use assistive devices such as water dumbbells, noodles, inflatable boards, and kickboards so as to engage their entire body in resistance exercise and provide needed support. They will also engage in aerobic activities such as aqua walking or jogging and plyometric activities such as skipping or single leg hopping while in the pool.* After the initial two months, participants may transition to a self-paced program with study staff-led exercise sessions repeated every 2 weeks for the duration of this 4-month phase. *For those veterans who do not wish to transition to a self-paced program, they will continue to attend group-based pool exercise at VAPAHCs. Those veterans who do transition to a self-paced program will have access to the VAPAHCs aquatic facilities during normal "drop-in" hours so that they may continue their thrice-weekly aquatic exercises.* After completion of the exercise-training portion of the intervention, participants will undergo a second series of assessments (i.e., Time 2 assessments). They will then transition to the cognitive training portion of the intervention. The "comprehensive extended" cognitive training program was selected because it has demonstrated efficacy in improvement of delayed recall of the proposed outcome measures (Yesavage et al., 2008). Veterans will participate in 4 weeks of cognitive training before completing the third and final series of assessments (i.e., Time 3 assessments).

*Participant safety is of the utmost importance. As such, ACSM-certified exercise physiologists will conduct all exercise sessions and cardiopulmonary testing. During pool-based work, exercise physiologists will be in the water with the veterans, guiding them through the exercises. All staff to veteran ratio will be in dictated by current ACSM standards. In addition to the ACSM-certified exercise physiologists, both Aquatic facilities are fully staffed with lifeguards certified in CPR for Professional Rescuers and Standard First Aid. Lifeguards will be on the pool deck and present during all pool-based exercises. Both Aquatic facilities feature fully operational crash carts that undergo regular inspections. All study and pool staff are trained in basic life support as well as fully knowledgeable of all safety procedures for the facility. Study and pool staff undergo regular facility led safety drills.*

Cognitive training classes will be taught by [name], who is a board certified geropsychologist with considerable expertise in cognition and cognitive training.

Sources of Materials. Data will come from multiple sources:

1. Semi-structured interviews

2. Cognitive Assessments
3. Participant self-report of demographic information, medical history, memory complaints, and physical activity
4. Collateral interviews
5. Physical examination
6. Cardiopulmonary exercise testing
7. Laboratory work-up
8. Biological and Genetic Measures

Only research staff that have completed appropriate training in protection of human subjects at VAPAHCS and Stanford University will have access to the data. Data will be collected using paper-and-pencil measures and by computer. Hard copies of data will be kept in a locked cabinet in locked offices at the MIRECC at VAPAHCS. Electronic data will be stored on a secure computer on password-protected files and coded by subject identifier/ number so that participants cannot be identified by their research record.

## **Potential Risks**

Exercise Testing. Exercise treadmill or bicycle tests will be performed to determine whether interested veterans are eligible for participation. There are rare instances of serious complications such as a heart attack, rhythm disturbance, or death. These occurrences are rare; however, happening in approximately 1 in 10,000 tests. There is also a slight risk of trauma secondary to falling. Additionally, participants may become fatigued or short of breath.

Psychiatric Testing. Psychiatric screening will be performed to determine whether the participant meets inclusion and exclusion criteria for the study. From past experience, potential risk to veterans is expected to be minimal. However, some questions asked during the interview or in the written questionnaires may be potentially distressing to the veterans or may cause them to think about traumatic events or problems that may be anxiety-provoking or upsetting. Veterans who develop suicidal intent will be treated following established procedures of VAPAHCS.

Cognitive Testing. There do not appear to be any significant risks associated with cognitive testing other than the commitment of significant time for participation. Some participants may experience some anxiety during and after the cognitive testing. Those veterans found to have significant cognitive impairment, and thus are excluded from participation in the proposed study, will be referred to the ACRC for a full diagnostic evaluation.

Laboratory Work-Up and Collection of Genetic Data. There is minimal risk of bruising, infection, or fainting from the blood draw to collect laboratory and genetic data. On very rare occasions there may be mild bleeding or bruising at the sampling site.

## **2. Adequacy of Protection Against Risks**

Recruitment and Informed Consent. Participants will be recruited via clinician referrals, media advertisements, and local veteran agencies. Depending on the referral source, potential participants will either call the Center or research staff will send a letter to interested participants informing them of the current study, providing them with a description of the study and with a contact number to volunteer for the study or to obtain further information. Those who volunteer will be invited to join the project and the nature of the experiment will be explained to them. Interested parties will be scheduled for a screening office visit during which informed consent process will be initiated. This will entail a discussion between the veteran and a trained clinician and / or research assistant. This discussion will highlight important aspects of the informed consent form such as details of the project, voluntary participation, and the risks and benefits of participation. Signatures will be obtained only after all questions have been adequately addressed. All participants will be treated in an ethical manner. The following sections describe the measures we will take to minimize risk to participants.

Exercise Testing. All exercise tests will be conducted in the state of the art VAPAHCS Exercise Testing Laboratory which is staffed by the Co-I ([name]), who is an expert in exercise physiology, as well as two research associates who each have extensive experience in exercise testing. The laboratory is located in the Cardiology division of the main hospital at VAPAHCS, thus if any emergency were to occur, appropriate staff

would be able to respond immediately. Additionally, if a participant becomes fatigued, short of breath, has chest pain, or desires to stop, the exercise treadmill test will be discontinued. All participants will be closely monitored by qualified staff during exercise treadmill testing and thus help can be provided immediately, if needed.

Exercise Training. Complications during exercise training are rare, even among individuals with existing heart disease. The American Heart Association has summarized the literature in this area and has suggested that a complication related to exercise (e.g., serious rhythm disturbance or myocardial infarction) occurs at a rate of once in every 62,000 hours of exercise. All exercise training will be performed using individualized prescriptions in accordance with established guidelines and overseen by trained exercise physiologists.

Psychiatric Screening. For both the psychiatric screening and cognitive testing, confidentiality is assured through the use of study participant ID numbers, and all files are kept in locked cabinets. Any computerized data will be identified by a study participant number. Any documents that obtain both the study participant identification number and the participant's name will be kept in a locked file cabinet separate from the study data. Participants may have their results forwarded to their physician or other health care provider at the participant's request. In the event of discomfort experienced during the psychiatric screening and/or cognitive testing, all participants will be informed that they are free to decline to answer any questions they do not wish to answer, or to stop the interview or testing at any time. Psychiatric screens will be done by psychiatry fellows at the MIRECC who are experienced and sensitive to clinical issues. Clinicians will be available in the case of an adverse event to debrief with the participant. Referrals to the outpatient mental health clinic will be available in the case of an adverse event.

Cognitive Testing. Same procedures as Psychiatric Screening (above).

Laboratory Work-up and Collection of Genetic Data. Because disclosure of genetic information could have psychological consequences, as well as affecting insurability and employment status of participants and/or their relatives, extreme caution is taken to prevent the inadvertent disclosure of genetic information. The consent form states that we do not divulge genetic information to participants, their caregivers, relatives, or their physicians. The actual clinical utility of all genetic testing which we perform at present is unknown. For this reason, it is impossible to provide genetic counseling as to the meaning of results to any individual subjects. Participants are, however, given free access to aggregate genetic data as it appears in publications. Participants are informed that if in the future it becomes possible to provide meaningful genetic counseling based on our results this service will be provided. We plan to follow the special genetic security procedures established at our Center for handling genetic information pertaining to dementia. We take these issues very seriously and will have all procedures followed under this project integrated with the established Center procedures that are summarized below.

Enhanced Security for Genetic Data. The purpose of these procedures is to ensure confidentiality of participant data, with particular reference to genetic information collected on all Center participants. Currently the number of genetic markers of interest to clinicians and researchers is limited but is expected to increase rapidly. Extra safeguards are provided so that this very private and potentially damaging information is carefully managed. We are sensitive to the potential impact of this information on medical insurability of participants and their children. Therefore, each Center participant is assigned a Patient ID number (PATID), and the following steps are taken:

- 1) The PATID is co-located with a participant's name only where absolutely necessary, e.g., on clinical charts and clinical scheduling records.
- 2) The Database Manager generates a Biosample ID number for each PATID.
- 3) The Biosample ID is used to identify biological samples for testing in independent laboratories, but no sample also contains the PATID, participant's name or social security number.
- 4) Laboratory results are provided to the Database Manager with the Biosample ID but not with the name. Participants' names or social security numbers are not in the central database. Only the Database Manager can match the Biosample ID with the PATID, and the Database Manager does not have access to participant's names.
- 5) Data analyses and print outs are provided by the Database Manager with PATIDs only in cases where original data are sent back to the investigator who collected it for verification of data integrity.

6) Typical data analyses, such as correlations that span multiple datasets, and printouts provided to investigators other than those who directly collected the data, are provided without PATIDs only after they complete the standard data request forms and the request has been approved.

Genetic data security meetings are held periodically for the Center. All PIs, collaborating investigators, and staff involved in the acquisition, handling, storage, or analysis of genetic data are required to attend. The following topics are discussed:

- Information contained in DNA samples.
- Informed consent for DNA samples and genotyping.
- How disclosure of genotypes could affect subjects.
- How disclosure of genotypes could affect relatives of subjects.
- How to respond to inquiries about genetic data.
- Security measures to prevent disclosure of genetic information.
- Transmission of genetic data among components of the Center.

All personnel collecting, managing, interpreting or receiving genetic data are required to sign a statement that they attended this meeting where the above topics were discussed.

In addition, we have created a formal Data Security Policy document which is followed by all researchers. All protected health information (PHI) can only be stored and accessed from a secure server.

Adverse Events and Serious Adverse Events. An Adverse Event (AE) is defined by the ICH for Clinical Safety Data Management as any untoward physical or psychological occurrence in a human subject participating in research. The AE does not necessarily have to have a causal relationship with the pharmacological product, study intervention or assessment. An AE can, therefore, be any unfavorable or unintended sign (including an abnormal laboratory finding), symptom or disease associated with the use of a medicinal (investigational) product. All AEs that commence during the treatment phase will be collected and followed until resolution OR for thirty days after the veterans participation in the study ends.

Serious Adverse Events (SAEs) are a subset of adverse events and are defined by the ICH for Clinical Safety Data Management as any untoward medical occurrence that:

- Results in death
- Is life-threatening
- Requires inpatient hospitalization or prolongation of existing hospitalization
- Results in persistent or significant disability or incapacity
- Is a congenital anomaly / birth defect or
- Any other condition that, based upon medical judgment, may jeopardize the subject and require medical or surgical treatment to prevent one of the above outcomes

All SAEs will be recorded, regardless of cause. Collecting and recording of SAEs will begin at randomization and will continue throughout the treatment phase. For a veteran who ends study participation prior to the study's completion date, SAEs will be monitored and reported 30 days after the "End of Study" date for that veteran or until the SAE is resolved.

Expedited Reporting of Serious Adverse Events (SAEs). Serious Adverse Event reports will be provided to the PI within 24 hours and the PI will review the SAE report to assess completeness of documentation and to determine whether the SAE requires that a safety report be filed (rare). If the SAE is not resolved at the time the event is reported, the study personnel must monitor and provide SAE follow-up information to the PI at least every 30 days OR until the SAE resolves. The study personnel must handle requests for SAE follow-up information in the same prompt manner the original SAE reports are handled. The PI will be responsible for

evaluating all SAEs for veteran safety concerns. Tables of AEs and SAEs will be generated and presented to the PI on a schedule set by the IRB and PI.

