Enrollment and Study Implementation. Study staff will explain the study to veterans and, if interested, the consent form and a one page project description will be mailed. Appointments will then be made for three days of evaluation. Day 1: informed consent; cognitive, psychological and functional screening; Day 2: neuropsychological and self-report measures; and Day 3: cardiopulmonary testing and biological measures. When these evaluations are completed, eligible participants will be scheduled for the first exercise session within two weeks. The exercise training portion of intervention is approximately 24 weeks. After completion of the exercise training, participants will be re-assessed with the cardiopulmonary exercise testing, cognitive measures, biological measures, outcome measures, and measures of physical activity. Participants will then begin four weeks of thrice weekly cognitive training classes at VAPAHCS. At completion of the cognitive training, participants will undergo the post-treatment assessment: cardiopulmonary exercise testing, cognitive measures, biological measures, outcome measures, and measures of physical activity. Participants will receive payments of \$50 for each set of assessments completed.

We plan to telephone screen 200 participants, based upon prior work (Myers et al., 2010; Yesavage et al. 2008), half or 100 are expected to proceed to an in-office evaluation (10 per month), half, or approximately 50 enrolled (5 per month). Dropouts will not be replaced as this is a feasibility study and an aim is to evaluate the appropriateness of the inclusion and exclusion criteria.

All in-house exercise sessions and activity surveillance will be supervised by exercise physiologists certified by the American College of Sports Medicine (ACSM). CT will be taught by the PI.

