### **Database Management and Planned Statistical Analyses**

Data Collection and Database Management. There are three proposed testing time points in this study: prior to randomization (T1), at the end of the exercise program and prior to beginning CT (T2), and at the end of the CT (T3). All identifying information will be removed as data are coded by a unique subject number/identifier. Only the PI and her designee will have access to the identifying information linking subject number to name. All data will be checked for completeness and every effort made to obtain missing data. Data storage will be on computerized password protected databases that are backed up nightly. Additionally, our MIRECC and associated laboratories are familiar with the relevant security and confidentiality issues pertaining to genetic materials and take extra safeguards to protect this information.

Data Analyses. Descriptive analyses of categorical variables will include frequency tables; we will compute measures of central tendency (mean, median, standard deviation, and interquartile range) for those continuous variables. Additionally we will examine the distribution of scores on dependent measures to test assumptions of normality and homogeneity of variance and thus make appropriate transformations when necessary.

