Specific Aim 1: WATER+CT will be feasible as shown by good recruitment and retention rates. Statistical Analyses: To test feasibility of the proposed project, the ratio of enrolled to completed participants will be calculated;  $\geq 80\%$  will be considered good retention. Specific Aim 2: To evaluate the appropriateness of suggested inclusion and exclusion criteria for the aims of the proposed project. Statistical Analyses: We will examine the reported adverse events for participants as well as reasons for screening failures (i.e., those who are consented but excluded from participation prior to randomization). Descriptive analyses of these data will include frequency tables and be used to provide justification for the proposed inclusion and exclusion criteria or to modify them appropriately. Specific Aim 3: To evaluate appropriateness of the WATER+CT for study goals. Statistical Analyses: Appropriateness of treatment conditions will be determined through examination of the participant adherence data. Adherence data will include information from pedometers, heart rate monitors, 7-day activity logs, and cognitive training homework logs. Adequate adherence to exercise prescriptions and CT homework will be defined as completion of  $\geq 80\%$  of assignments as defined by self-report and trainer observation. Specific Aim 4: To assess outcome measurement techniques for participant rate of response in WATER+CT. Statistical Analyses: As this is a single-arm trial, a direct comparison between the WATER + CT condition and a comparative condition is not possible. Participants response rate will be determined by examining the percentage of participants who evidence clinically relevant change after study participation. To determine what a clinically relevant difference in the primary outcome measure (delayed recall of a Word List) would be, we reanalyzed data from our initial clinical trial (Yesavage et al., 2008). Our strategy was to look in that study at the difference in baseline scores between 60 year olds and 70 year olds on the same measure as the proposed work. We found that the difference was 1.7 words. We believe that showing such a difference would be clinically meaningful insofar as it represents a decade of aging's effects on memory. This will be an intent-to-treat analysis, thus all data will be analyzed. Specific Aim 5: To examine outcome "moderator" and "mediator" measurement techniques to determine: a) in whom and under what conditions clinically relevant change occurs and b) the mechanisms through which clinically relevant change occurs. Here we are referring to within subjects effects. Statistical Analyses: Multiple regression modeling will be performed in a preliminary manner to examine individual differences in treatment response depending on baseline (T1) characteristics (age, level of education, APOE and BDNF genotypes). A significant Response Rate X Moderator interaction indicates a differential response rate, e.g., the response rate depends upon age. Such measures are "moderator" variables, i.e., they are used to determine on whom or under what conditions improvement occurs. Additional analyses will be performed to examine the extent to which individual differences in the efficacy of CT treatments depend upon changes in cardiovascular functioning, BDNF plasma levels, and changes in efficiency of working memory (Digit Span) during combined aerobic and resistance exercise training (T1 to T3). These analyses use changes in these two measures as "mediator" variables, i.e., they are used to determine how or why improvement occurs.

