
Project Management. To support the Specific Aims stated above, the investigators will perform appropriate tasks within the funding period. The first two months of the funding period (Start-Up Phase) will be devoted to hiring and training of research staff and purchasing activity monitoring devices. The Data Collection Phase will begin in Month 3 and continue through Month 20 to allow adequate time for participants to complete the 8-month long intervention. We will randomize five veterans a month through Month 13. Finally, the Study Close-out Phase will begin in Month 21 with Data Analysis and Manuscript Preparation. These will activities will be completed within Month 24.

**Human Subjects Involvement and Characteristics.** Involvement of human subjects in the proposed study includes participation in a feasibility study of an water-based physical exercise plus cognitive training adjunctive treatment for Mild Cognitive Impairment (MCI) in older veterans. We expect to enroll a total of 50 veterans, age 50 years old to 90, in this study. Using the criteria put forth by Alberts et al (2011), all veterans will be classified as having amnestic MCI. These veterans will be recruited through clinician referral, media advertisement, and local veteran agencies. Participants will also be recruited from the outpatient clinics of the VA Palo Alto Health Care System (VAPAHCS) as well as the Stanford / VA Aging Clinical Research Center (ACRC).

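### AE and SAE recording opens only after the eligibility exercise test, so events at that first study-mandated test fall outside both recording windows

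*Combined protocol and SAP*

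**What the plan says.** Under Adequacy of Protection Against Risks, the Adverse Events paragraphs set two start points. For non-serious events, "All AEs that commence during the treatment phase will be collected". For serious events, "Collecting and recording of SAEs will begin at randomization and will continue throughout the treatment phase".

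The order of study steps is set elsewhere:

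- Research Design, Enrollment and Study Implementation, puts informed consent on Day 1 and "Day 3: cardiopulmonary testing and biological measures". Only after these evaluations does it say that "eligible participants will be scheduled for the first exercise session within two weeks".
- Database Management and Planned Statistical Analyses places the first assessment point "prior to randomization (T1").
- The Study Procedures paragraph has the same order: "Once recruited and successfully screened (i.e., Time 1 assessments), participants will meet with the study staff to develop an exercise prescription".
- Potential Risks states that the exercise test is done to decide eligibility. It lists cardiac complications and death at about 1 in 10,000 tests, and also falls, fatigue and breathlessness. For the blood draw it lists fainting and bruising.

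**The concern.** The plan foresees events at the screening exercise test and the screening blood draw, but its recording rules open only after both. A veteran who has consented and is then harmed during a procedure the study requires would have no AE or SAE record under the rules as written. The 24-hour report to the investigator acts on SAE reports, so nothing in the text requires it for such an event either.

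The gap also touches a stated aim. Aim 2 judges the inclusion and exclusion criteria from reported adverse events and reasons for screening failure, and inability to take an exercise stress test is itself an exclusion criterion. Events at that test are direct evidence on it. The treadmill or bicycle test is also given to people selected because weight-bearing exercise is difficult for them.

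**Working it through.** **Order of events**

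1. Consent: Day 1.
2. First exercise test and blood draw: Day 3, part of T1.
3. Eligibility decision and enrolment: after T1.
4. First exercise session: planned within two weeks of the evaluations. I take this as the start of the treatment phase, which the protocol does not define.

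**Can randomization be read so that the SAE window covers step 2?** A single-arm trial has no randomization. The nearest reading is enrolment: Project Management says "We will randomize five veterans a month through Month 13", and Research Design expects about 50 enrolled at 5 per month. Enrolment cannot mean consent, because those 50 are what remains of 100 in-office evaluations, and consent is taken at the first evaluation visit. Aim 2 confirms the order by describing screening failures as "those who are consented but excluded from participation prior to randomization". On either reading the SAE window opens after step 2. The AE window opens at step 4, so for non-serious events the gap runs on to the first session.

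**Does other text open the window?** The sentence requiring all SAEs to be recorded whatever their cause concerns causality, and the next sentence fixes the start. The exercise-testing safeguards describe a staffed hospital laboratory, monitoring and stopping of the test. The psychiatric-screening safeguards describe debriefing and referral. None is a recording rule, and nothing in the document starts collection at consent.

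**Scale: serious events at T1**

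- Inputs: 1 in 10,000 tests (Potential Risks); 50 tests if only those later enrolled reach Day 3, or 100 if nobody fails on Day 1 or Day 2 (Research Design).
- Expected events: 50 × 0.0001 = 0.005; 100 × 0.0001 = 0.010.
- Chance of at least one: 1 − (1 − 0.0001)^50 = 0.50%; 1 − (1 − 0.0001)^100 = 1.0%.

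**T1 share of all expected serious exercise complications** (full attendance, no dropout, T2 and T3 tests counted as covered)

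- Training: 50 veterans × 3 sessions per week × 24 weeks = 3,600 sessions. At 30 to 45 minutes this is 1,800 to 2,700 hours. At the stated 1 per 62,000 hours it gives 0.029 to 0.044 events.
- T2 and T3: 100 tests × 0.0001 = 0.010.
- Lowest share: 0.005 / (0.005 + 0.010 + 0.0435) = 8.5%. Highest share: 0.010 / (0.010 + 0.010 + 0.0290) = 20.4%.
- Study total: 0.005 + 0.010 + 0.029 = 0.044, up to 0.010 + 0.010 + 0.0435 = 0.064.
- With the five-minute warm-up and five-minute cool-down added, sessions last 40 to 55 minutes. That gives 2,400 to 3,300 hours, 0.039 to 0.053 training events and a T1 share of about 7% to 17%.
- By number of tests, T1 is 50 of 150 (one third) to 100 of 200 (one half) of all planned exercise tests.

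**Non-serious events.** The documents give no rate. Purely as an illustration, an assumed 1% to 5% per test would put 50 × 0.01 = 0.5 to 100 × 0.05 = 5 events outside the windows.

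**The case against.** The consequence is small. At most 0.010 serious events are expected, supervision of the test is sound, and an event that leads to exclusion can still appear in Aim 2 as a reason for screening failure. What is lost is the AE or SAE classification of such exclusions, and events in veterans who still go on to enrol. Recruitment, retention, adherence and response-rate analyses are untouched. This stands, and it limits the severity.

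Other text also suggests careless wording rather than a decision to ignore screening events. The AE definition covers anyone taking part in the research and mentions assessments. Aim 2 sets no phase limit on adverse events, and a DSMB reviews safety and data quality each year. None of this opens the window, however, and a board can review only what has been collected. The broad definition makes the gap plainer: these events count as AEs, yet the collection rule leaves them out.

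The 1% to 5% rate has no anchor in the documents, and the T1 share shifts with the session length used. Both points are fair, and the conclusion depends on neither figure.

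Finally, consent-based collection would extend follow-up to some 50 screen failures who have no stated end-of-study date. The existing rule can still be applied, because their participation ends at exclusion and only those with an event need follow-up.

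**Conclusion.** The concern holds, with high confidence, because it rests on the protocol's own sequence of steps. Events at the first exercise test and blood draw fall outside both recording windows, whether randomization is taken literally or as enrolment. The expected serious-event count is 0.005 to 0.010, which assumes the stated complication rate applies to this population and that 50 to 100 veterans take the test. The non-serious count cannot be estimated from the documents. This is a gap in safety recording that should be fixed. It does not show inadequate supervision, and it does not affect the efficacy or feasibility calculations.

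**What to change.** In the Adverse Events and Serious Adverse Events paragraphs, replace both start points with signed informed consent (Day 1), stating that all screening procedures are included. This also removes the undefined randomization trigger. Keep the existing follow-up and reporting rules, and state that for a screen failure participation ends on the date of exclusion. Tabulate events during screening procedures separately, including those in screen failures, and name that table as an input to Aim 2.

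The same edit should say whether the T3 exercise test lies inside the window. The protocol calls T3 post-treatment, and the figures above assume that it is covered.

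The cost is protocol wording, a few extra case-report entries and follow-up of any screen failure who has an event. No new staff, visits or procedures are needed.
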